## **10.3 Monitoring of the Study**

The clinical monitor, as a representative of MedTrials Inc. and/or OncoNano Medicine, has the obligation to follow the study closely. In doing so, the monitor will visit the principal investigator and study facility at periodic intervals, in addition to maintaining necessary contact through telephone, email, and letter. The monitor will maintain current personal knowledge of the study through observation, review of study records and source documentation, and discussion of the conduct of the study with the principal investigator and staff.

All aspects of the study will be carefully monitored, by MedTrials Inc., OncoNano Medicine or a designee, for compliance with applicable government regulation with respect to current International Conference on Harmonisation (ICH) harmonised tripartite guideline E6(R1): Good Clinical Practice and current standard operating procedures.

#### **10.4 Inspection of Records**

The principal investigator and institutions involved in the study will permit trial-related monitoring, audits, institutional review board (IRB) review, and regulatory inspection(s) by providing direct access to all study records. In the event of an audit, the principal investigator agrees to allow MedTrials Inc., OncoNano Medicine, representatives of OncoNano Medicine, the United States Food and Drug Administration (FDA), and/or other regulatory agency access to all study records.

The principal investigator should promptly notify MedTrials and OncoNano Medicine of any audits scheduled by any regulatory authorities and promptly forward copies of any audit reports received to MedTrials Inc. and OncoNano Medicine.

#### **10.5 Study Record Retention**

Essential documents should be retained until at least 2 years after the last approval of a marketing application in an ICH region and until there are no pending or contemplated marketing applications in an ICH region or at least 2 years have elapsed since the formal discontinuation of clinical development of the investigational product. These documents should be retained for a longer period, however, if required by the applicable regulatory requirements or by an agreement with MedTrials Inc. and/or OncoNano Medicine. It is the responsibility of MedTrials Inc. and OncoNano Medicine to inform the principal investigator as to when these documents no longer need to be retained.

### **11. ADMINISTRATIVE CONSIDERATIONS**

The following administrative items are meant to guide the principal investigator in the conduct of the trial but may be subject to change based on industry and government standard operating procedures or working practice documents or guidelines. Administrative changes will be reported to the IRB but will not result in protocol amendments.

#### **11.1 Confidentiality**

All laboratory specimens, evaluation forms, reports, and other records will be identified in a manner designed to maintain subject confidentiality. All records will be kept in a secure storage area with limited access. Clinical information will not be released without the written permission

of the subject (or the subject's guardian), except as necessary for monitoring and auditing by OncoNano Medicine, its designee, the FDA, or the IRB.

The principal investigator and all employees and coworkers involved with this study may not disclose or use for any purpose other than performance of the study, any data, record, or other unpublished, confidential information disclosed to those individuals for the purpose of the study. Prior written agreement from OncoNano Medicine or its designee must be obtained for the disclosure of any said confidential information to other parties.

## **11.2 Institutional Review Board/Ethics Committee Approval**

Federal regulations and the ICH guidelines require that approval be obtained from an IRB before participation of human patients in research studies. Before the study onset, the protocol, informed consent, advertisements to be used for subject recruitment, and any other written information regarding this study to be provided to the subject or the subject's legal guardian must be approved by the IRB. Documentation of all IRB approvals and of the IRB compliance with ICH E6(R1) will be maintained by the site and will be available for review by OncoNano Medicine or its designee.

All IRB approvals should be signed by the IRB chairman or designee and must identify the IRB name and address, the clinical protocol by title and/or protocol number and the date approval and/or favorable opinion was granted.

The principal investigator is responsible for obtaining continued review of the clinical research at intervals not exceeding 1 year or otherwise specified by the IRB. The principal investigator must supply OncoNano Medicine or its designee with written documentation of continued review of the clinical research.

## **11.3 Modification of the Protocol**

Any changes in this research activity, except those necessary to remove an apparent, immediate hazard to the subject, must be reviewed and approved by OncoNano Medicine or its designee. Amendments to the protocol must be submitted in writing to the principal investigator's IRB for approval before patients are enrolled into an amended protocol.

## **11.4 Informed Consent**

A written informed consent in compliance with Part 50 of Title 21 of the Code of Federal Regulations (CFR) shall be obtained from each subject before entering the study or performing any unusual or nonroutine procedure that involves risk to the subject. An informed consent template may be provided by OncoNano Medicine to investigative sites. If any institution-specific modifications to study-related procedures are proposed or made by the site, the consent should be reviewed by OncoNano Medicine and/or its designee, if appropriate, before IRB submission. Once reviewed, the consent will be submitted by the principal investigator to their IRB for review and approval before the start of the study. If the informed consent form is revised during the course of the study, all active participating patients must sign the IRB-approved revised form.

Before recruitment and enrollment, each prospective subject will be given a full explanation of the study and allowed to read the approved informed consent form. Once the principal investigator is assured that the subject understands the implications of participating in the study, the subject will be asked to give consent to participate in the study by signing the informed consent form.

The principal investigator shall provide a copy of the original form of the signed informed consent to the subject and/or legal guardian.

### **11.5 Protocol Violations and Deviations**

The principal investigator or designee must document and explain in the subject's source documentation any deviation from the approved protocol. The principal investigator may implement a deviation from or a change of the protocol to eliminate an immediate hazard to trial patients without prior IRB approval. As soon as possible after such an occurrence, the implemented deviation or change, the reasons for it, and any proposed protocol amendment(s) should be submitted to the IRB for review and approval, to OncoNano Medicine for agreement, and to the regulatory authorities, if required.

A deviation from the protocol is an unintended and/or unanticipated departure from the procedures and/or processes approved by OncoNano Medicine and the IRB and agreed to by the principal investigator. Deviations usually have an impact on individual patients or a small group of patients and do not involve inclusion/exclusion or primary endpoint criteria. A protocol violation occurs when there is nonadherence to the protocol that results in a significant, additional risk to the subject, when the subject or principal investigator has failed to adhere to significant protocol requirements (inclusion/exclusion criteria) and the subject is enrolled without prior approval by OncoNano Medicine, or when there is nonadherence to FDA regulations and/or ICH E6(R1) guidelines.

The clinical monitor will document protocol violations and deviations throughout the course of monitoring visits. The monitor will notify the principal investigator during a visit and/or in writing of all violations and deviations. The IRB should be notified of all protocol violations and deviations in a timely manner.

### **11.6 Study Reporting Requirements**

By participating in this study, the principal investigator agrees to submit reports of SAEs according to the timeline and method outlined in the protocol. In addition, the principal investigator agrees to submit annual reports to their IRB as appropriate. The principal investigator also agrees to provide OncoNano Medicine with an adequate report shortly after completion of the principal investigator's participation in the study.

### **11.7 Investigator Documentation**

Before beginning the study, the principal investigator will be asked to comply with ICH E6(R1) 8.2 and 21 CFR by providing the following essential documents, including but not limited to:

- An original investigator-signed Investigator Agreement page of the protocol.

- An IRB-approved informed consent, samples of site advertisements for recruitment for this study, and any other written information regarding this study that is to be provided to the subject or legal guardians.
- IRB approval.
- Form FDA 1572, fully executed, and all updates on a new fully executed Form FDA 1572.
- Curriculum vitae (CV) for the principal investigator and sub-investigators listed on Form FDA 1572. Current licensure must be noted on the CV. They will be signed and dated by the principal investigator at study start-up, indicating that they are accurate and current.
- Financial disclosure information to allow OncoNano Medicine to submit complete and accurate certification or disclosure statements required under 21 CFR 54. In addition, the investigators must provide to OncoNano Medicine a commitment to promptly update this information if any relevant changes occur during the course of the investigation and for 1 year following the completion of the study.
- Laboratory certifications and reference ranges for any local laboratories used by the site, in accordance with 42 CFR 493.

## **11.8 Study Conduct**

The principal investigator agrees that the study will be conducted according to the principles of the ICH E6(R1) guidelines and the principles of the World Medical Association Declaration of Helsinki. The principal investigator will conduct all aspects of this study in accordance with all national, state, and local laws or regulations.

## **11.9 Publications**

Following completion of the study, the data may be considered for reporting at a scientific meeting or for publication in a scientific journal. In these cases, OncoNano Medicine will be responsible for these activities and will work with the investigators to determine how the manuscript is written and edited, the number and order of authors, the publication to which it will be submitted, and other related issues. OncoNano Medicine has final approval authority over all such issues.

Data are the property of OncoNano Medicine and cannot be published without prior authorization, but data and publication thereof will not be unduly withheld.

**13. APPENDIX 1: SCHEDULE OF EVENTS**

Evaluation	Screening	Dosing		Treatment		
	Days -30 to -1	Day 0 Pre-Dose	Day 0 Post-Dose	Surgery	Day of Discharge	Day 21 (± 10 Days)
Informed consent & subject enrollment	X					
Inclusion/exclusion criteria	X	X				
Pregnancy test a	X	X				X
Demographic data	X					
Medical history	X					
Physical examination	X				X	X
Karnofsky Performance Status	X					
Height b	X					
Body weight b	X	X				
Vital signs c	X	X	X d	X	X	X
12-lead electrocardiogram		X				X
Concomitant medications	X	X	X	X	X	X
Study drug administration			X e			
Adverse events review f			X	X	X	X
Serum chemistry	X	X		X	X	X
Hematology g	X	X		X	X	X
Surgery				X		
Intraoperative Imaging				X		
Pathology evaluation of surgical specimens					X h	

**Footnotes**

- a For female patients, a serum sample or urine dipstick for a pregnancy test will be collected at screening and on Day 0 and Day 21.
- b Body mass index will be calculated at Screening only.
- c Vital sign measurements will include systolic and diastolic blood pressure, pulse, respiratory rate, and temperature (in degrees Celsius). Blood pressure and pulse will be measured after a resting period of at least 5 minutes in the supine position.
- d Patient's vital signs are to be recorded immediately after the infusion and 30 minutes afterward
- e The Sponsor recommends the use of prophylactic diphenhydramine prior to study drug administration, in an effort to reduce the prevalence of infusion-related reactions.
- f Patients will be assessed for AEs occurring from the time of dosing through Day 21 ( $\pm 10$  days)
- g Hematology assessments may include hemoglobin, hematocrit, erythrocyte count (red blood cells), differential leukocytes, platelet count, and total leukocytes (white blood cells).
- h Pathologic analysis of surgical specimens will take place from the conclusion of surgery and up to 10 days after

## **14. APPENDIX 2: FDA-CLEARED NIR IMAGING DEVICES**

**NOTE:** this list is not comprehensive and does not restrict the use of other FDA-cleared imaging device from use in this trial.

### **14.1 NOVADAQ SPY Elite**

The NOVADAQ SPY Elite system is an active device used for intraoperative fluorescence imaging. The device is developed for open surgery. The device uses visible (white light) and NIR spectra in real-time to visualize circulation and ICG based tumor detection. The device is commercially available and 510(k) cleared by the FDA for surgical use.

### **14.2 NOVADAQ SPY-PHI**

The NOVADAQ SPY-PHI (Portable Handheld Imaging) system is an active device used for fluorescence imaging. The device uses both visible (white light) and NIR spectra, which can be used for visualization of circulation and ICG-based tumor detection during several (surgical or non-surgical) procedures. The device is commercially available and 510(k) cleared by the FDA for surgical use.

### **14.3 NOVADAQ PINPOINT**

The NOVADAQ PINPOINT is an intraoperative laparoscopic fluorescence imaging system, used in conjunction with an injected ICG based fluorescent imaging agent, to assess perfusion and visualize structural anatomy using visible (white light) and NIR during cardiothoracic, gastrointestinal, breast, and other reconstructive surgical procedures.

### **14.4 da Vinci Firefly**

The da Vinci Firefly system (Intuitive Surgical, California, USA) provides real-time NIR guidance through visualization of injectable fluorescence dye. The device uses visible (white light) and NIR spectra in real-time to visualize circulation and ICG based tumor detection. The device is commercially available and FDA-cleared for visual assessment of vessels, blood flow, and related tissue perfusion using NIR imaging.

### **14.5 Visionsense Iridium**

The Visionsense Iridium camera system (Visionsense, Philadelphia, PA, USA) uses 3DHD technology intra-operatively for real-time infrared fluorescence and white light imaging visualization during live surgery to enhance anatomical feature identification.

SUSAR	Suspected Unexpected Serious Adverse Reaction
SWI	Sterile Water for Injection
TBR	Tumor-to-Background Ratio
TEAE	Treatment-Emergent Adverse Event
VATS	Video-Assisted Thorascopic Surgery
WMA	World Medical Association

1. INTRODUCTION

This Statistical Analysis Plan covers the statistical analysis and reporting for the protocol ON-1005 version 02 dated 25JAN2022. A detailed list of tables, listings and figures (TLFs) will be supplied in a separate, version-controlled document.

In case of discrepancies between the SAP and the protocol, the SAP will overrule the protocol with respect to analyses and reporting. Any deviations from the protocol will be documented at the end of this document.

2. STUDY OBJECTIVES

2.1 Objectives and Endpoints

The primary objective of this study is to investigate whether pegasitacianine can detect clinically significant events (CSEs) at the patient level, which include:

1. The detection of disease that cannot be detected using standard procedures during the surgical resection of lung malignancies
2. The detection of synchronous lesions
3. The detection of positive surgical margins following primary tumor resection
4. Tumor-negative standard of care (SOC) biopsies

Table 1. Objectives and Endpoints

Objectives	Endpoints
Primary Objective	Primary Endpoint
The primary objective of this study is to investigate whether pegasitacianine can detect clinically significant events (CSEs) at the patient level.	Rate of CSEs, which include: 
1. The detection of disease that cannot be detected using standard procedures during the surgical resection of lung malignancies2. The detection of synchronous lesions3. The detection of positive surgical margins following primary tumor resection4. Tumor-negative standard of care (SOC) biopsies

Secondary Objectives	Secondary Endpoints
Determine sensitivity, specificity, negative predictive values (NPPV), and positive predictive values (PPV) of the imaging agent at the level of the individual specimens, including lymph nodes.	Sensitivity, specificity, negative predictive values (NPV), and positive predictive values (PPV) at the specimen-level.
Evaluate safety and toxicity of pegsitacianine.	Incidence of TEAEs and SAEs, abnormalities in lab values, vital signs, or ECG results.
Exploratory Objectives	Exploratory Endpoints
Assess the how the SBR affects the diagnostic accuracy of pegsitacianine in detection of metastatic disease vs. normal tissue.	ROC analysis across various tumor-to-background ratio fluorescence thresholds.
Effect of camera system on diagnostic results.	Diagnostic results across various camera systems.
Assess amount of fluorescence shown in various types of specimens.	Mean fluorescence intensity and Specimen-to-background ratio

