#### **7.6.2 Laboratory Measurements**

Blood hematology and serum chemistry tests may be performed using the standard panel of each institution (it is not necessary to add analytes if not part of standard panel unless ordered/recommended by treating physician). The following clinical laboratory parameters are an example of what is to be collected:

Clinical Chemistry	Hematology
Total protein	Hemoglobin
Albumin	Hematocrit
Blood urea nitrogen (BUN)	Erythrocyte count (red blood cells)
Calcium (total and ionized)	Differential leukocytes
Creatinine	Platelet count
Creatine kinase	Total leukocytes (white blood cells)
Chloride	
Total bilirubin	
Alkaline phosphatase	
Glucose	
Sodium	
Potassium	
Inorganic phosphate	
Lactate dehydrogenase	
Total Cholesterol	
Gamma-glutamyl transferase	
Alanine aminotransferase (ALT)	
Aspartate aminotransferase (AST)	

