5.2 Safety Endpoints

- TEAE incidence, severity, and relationship to study drug
- Physical examination results
- Vital signs results
- ECG results
- Clinical laboratory values (hematology and serum chemistry)

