7.11.2 Laboratory Data

The clinical laboratory data will be summarized by scheduled time point, Part, and change from baseline. Any laboratory data below/above the limit of quantification will be summarized using the value of the limit of quantification (upper or lower, respectively). A listing will be provided where the values that are below the lower limit or above the upper limit of the reference range will be flagged. Those values or changes in values that are considered clinically significant by the investigator will also be flagged in the listing.

Repeated or unscheduled results will not be included in the by timepoint summaries but will be included when looking for extreme values and displayed in the individual data listings.

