7.11.3 Vital Signs

Vital signs data will be summarized by time point, Part, and change from baseline. A listing will also be provided.

Repeated or unscheduled results will not be included in the summary statistics but will be included in the individual data listings.

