7.11.5 ECG

ECG results will be provided as a listing.

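### The SAP lists laboratory, vital-sign and ECG abnormalities as a secondary safety endpoint but plans no count of patients who have one

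*SAP*

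**What the plan says.** SAP 2.1, Table 1, sets against the objective of evaluating safety and toxicity the endpoint "Incidence of TEAEs and SAEs, abnormalities in lab values, vital signs, or ECG results". SAP 5.2 describes the same domain differently, as values and results: for example "Clinical laboratory values (hematology and serum chemistry", with no mention of abnormality.

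The planned analyses are:

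- **Laboratory (SAP 7.11.2):** "The clinical laboratory data will be summarized by scheduled time point, Part, and change from baseline". Out-of-range results are handled in a listing, where "values that are below the lower limit or above the upper limit of the reference range will be flagged"; results the investigator considers clinically significant are flagged there too. Repeated or unscheduled results are left out of the by-visit summaries but "will be included when looking for extreme values and displayed in the individual data listings".
- **Vital signs (SAP 7.11.3):** "Vital signs data will be summarized by time point, Part, and change from baseline", plus a listing. Unscheduled results appear in the listing only.
- **ECG (SAP 7.11.5):** "ECG results will be provided as a listing".

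SAP 7.2 defines a continuous summary as mean, SD, median, quartiles, minimum and maximum. On the data side, Protocol 7.6 allows local and/or central laboratories, and Protocol 7.6.2 says that the tests "may be performed using the standard panel of each institution". Protocol 7.5 has the investigator or designee judge each ECG against reference limits and for clinical significance, and record this in the eCRF.

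**The concern.** An endpoint about abnormalities asks how many patients had one. A summary of values by visit answers a different question, and a listing leaves the reader to do the counting without a stated rule. Three things are missing from the SAP text: a criterion for abnormality in each domain, a numerator that takes each patient's worst post-dose result, and a denominator.

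The liver tests show why this matters. Protocol 4.3 reports transient rises in 4 patients in the first study, with ALT up to 7 times, AST up to 10 times and alkaline phosphatase up to 3 times ULN. They were judged unrelated to study drug and put down to the length of surgery and anesthesia. Whatever their cause, a finding confined to a few patients is described by a count of patients and their worst values. The next study's planners will want that number, and under the SAP as written no table supplies it.

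**Working it through.** **Step 1. Endpoint against analysis.**

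| Domain | Named in Table 1 | Planned output | Abnormality criterion | Patients, n (%) |
|---|---|---|---|---|
| Laboratory | Yes | By-visit summary, change from baseline, flagged listing | Reference range and investigator's judgment, for listing flags only | None |
| Vital signs | Yes | By-visit summary, change from baseline, listing | None | None |
| ECG | Yes | Listing | None in the SAP, though a judgment is recorded in the eCRF | None |

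Protocol 9.7 has the same gap for laboratory data: values are flagged and not counted. The documents give no figure for this endpoint, so there is none to reproduce.

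**Step 2. Size of the Phase 1 finding.** The numerator of 4 is from Protocol 4.3. The denominator of 30 is the Phase 1a and 1b total in the same section; I take it to apply to this statement. For x of n, the exact (Clopper-Pearson) 95% limits are the 0.025 quantile of Beta(x, n−x+1) and the 0.975 quantile of Beta(x+1, n−x).

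- 4/30 = 13.3%, exact 95% CI 3.8% to 30.7%.
- Expected at N = 40: 40 × 4/30 = 5.3 patients.
- Chance of at least one: 1 − (1 − 4/30)^40 = 99.7%. At the lower confidence limit it is 78.4%.

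**Step 3. What the planned laboratory table would show.** Assume k of 40 patients peak at a multiple P of ULN at one scheduled visit and the others sit at b = 0.5 to 0.6 times ULN. The mean is b + (P − b) × k/40.

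| k | P (× ULN) | Mean (× ULN) | Maximum (× ULN) |
|---|---|---|---|
| 1 | 7 | 0.66 to 0.76 | 7 |
| 2 | 7 | 0.83 to 0.92 | 7 |
| 5 | 3 | 0.81 to 0.90 | 3 |
| 5 | 5 | 1.06 to 1.15 | 5 |
| 5 | 7 | 1.31 to 1.40 | 7 |

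One or two large rises, or five moderate ones, leave the mean within range; five at 5 or 7 times ULN do not. The maximum shows the peak in every row. It is the same for one, two or five patients at 7 times ULN, so it cannot say how many were affected. If the peak falls on an unscheduled draw, neither the mean nor the maximum in the by-visit table includes it.

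**Step 4. What a count would give at N = 40 (exact 95% CI).**

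- 0/40 = 0% (0% to 8.8%)
- 1/40 = 2.5% (0.1% to 13.2%)
- 3/40 = 7.5% (1.6% to 20.4%)
- 5/40 = 12.5% (4.2% to 26.8%)

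Enrolment is up to 40, so the final number may be lower: with none affected, the upper limit is 11.6% at n = 30 and 16.8% at n = 20.

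**The case against.** The case for leaving the plan alone has substance.

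- A reader might infer that only means are planned and that a liver signal would be averaged away. The documents do not support that. SAP 7.2 requires SD, quartiles, minimum and maximum. With five of 40 patients at 5 times ULN and the rest at 0.5, the table would show a mean of (35 × 0.5 + 5 × 5)/40 = 1.06, an SD of about 1.5 and a maximum of 5. That does not look normal.
- A reader might also infer that the endpoint is never calculated. That cannot be shown. SAP 1 places the detailed list of tables and listings in a separate document that was not available, and SAP 7.11.2 refers to a look for extreme values that may correspond to a table there.
- Protocol 8 allows laboratory findings to be recorded as adverse events with CTCAE grades, and SAP 7.11.1 tabulates treatment-emergent events by grade. Those cases are counted.
- It is unclear whether incidence in Table 1 governs abnormalities as well as adverse events.
- This is a descriptive single-arm pilot, and a flagged listing of 40 patients can be counted by hand.

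Most of this stands, and it narrows the point without removing it. A table list should carry out the SAP, not supply a missing endpoint definition. However the sentence in Table 1 is parsed, abnormalities are what it names. Adverse-event tables catch only what the investigator chose to report. Phase 1 suggests this can matter: Protocol 4.3 lists the events reported in 4 or more patients, and no liver-enzyme term is among them although 4 patients had rises. Either not all were recorded as events, or they were split across terms. Counting by hand from a listing, with no criterion fixed beforehand, lets the rule be chosen after the data are seen.

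**Conclusion.** The point holds as a mismatch between a named endpoint and its planned analysis. Following the SAP text yields no number or percentage of patients with a laboratory, vital-sign or ECG abnormality. Unscheduled laboratory peaks reach only the listings and an extreme-value review with no threshold, output or denominator.

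The consequence is modest. Scheduled peaks would be visible as maxima, and reported events would be counted. What is lost is the number of patients affected, chiefly for abnormalities not reported as adverse events. At the Phase 1 rate that could be about 5 patients in 40, but the interval of 3.8% to 30.7% is wide, the earlier rises were judged unrelated to study drug, and nothing here shows that the agent harms the liver.

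The conclusion about the text rests on the SAP and protocol alone. The figures for the by-visit means rest on the assumed values in the working. Mixing of reference ranges is possible, not certain, since a central laboratory may be used.

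**What to change.** - **SAP 7.11.2:** add n/N (%) of patients by worst post-dose ALT, AST, alkaline phosphatase and bilirubin, in multiples of the performing laboratory's ULN, with unscheduled values included. Add low/normal/high shift tables for the other analytes. These would replace the undefined extreme-value review.
- **SAP 7.11.3:** add n/N (%) of patients with a vital-sign abnormality, against a criterion written down before the data are reviewed.
- **SAP 7.11.5:** add n/N (%) of patients with normal, abnormal and clinically significant ECGs at Day 0 and Day 21, from the assessments already in the eCRF.
- **Throughout:** take as N the patients with that test measured, because sites may use their own panel, and give exact 95% intervals.

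If the sponsor does not want these tables, Table 1 should be reworded to match the descriptive plan.

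The cost is a few extra tables from data largely collected already; Protocol 11.7 requires sites to supply reference ranges for local laboratories. The small drawback is that denominators may differ between analytes, which the tables should show openly.
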